2 AIMS

We propose a pilot study to determine the acceptability, feasibility and potential efficacy of a single ketamine infusion in adolescents and young adults with OCD. Promising data will lead to a grant application to the National Institutes of Mental Health for a fullscale randomized controlled trial.

Aim 1. To assess the feasibility/tolerability of using ketamine in adolescents with OCD Aim 2. To assess the effects of ketamine on OCD severity

3 PROCEDURES

We will recruit 5 adolescents and young adults (post-pubertal, ages 14-20) with OCD using similar criteria as in our prior ketamine study (Rodriguez et al. 2013) with the modification that participants have attempted at least one trial of a standard treatment (i.e., SRI and/or CBT). They will be free of medication and have at least moderate OCD severity (rating on Children's Yale-Brown Obsessive-Compulsive Scale [CY-BOCS] of at least 16) and near constant obsessions. After baseline assessment and evaluation, patients will receive a single infusion of intravenous ketamine 0.5 mg/kg. Obsessional severity will be evaluated at baseline, during the ketamine infusion and during post-infusion observation using the OCD-Visual Analogue Scale; OCD severity will be evaluated using the Children's Yale-Brown Obsessive Compulsive Scale (CY-

BOCS) and Yale-Brown Obsessive Compulsive Challenge Scale (Y-BOCCS) at weekly intervals for 2 weeks and 3-months following after the infusion; illness severity will be rated using the Clinical Global Impressions Severity Scale (CGI-S) at weekly intervals for 2 weeks and 3-months following after the infusion.

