In this study, we will evaluate the feasibility, tolerability, and preliminary efficacy of ketamine, a medication that modulates glutamate in the brain, as a rapid treatment for OCD symptoms in adolescents and young adults with OCD. Our rationale for using ketamine is threefold. First, glutamatergic abnormalities in corticostriatal circuits may underlie OCD symptoms based on human imaging, genetic, and animal studies; ¹⁻³ striatal glutamatergic levels have been associated with OCD severity. ^{4, 5} Thus, medications that modulate glutamatergic neurotransmission (e.g., riluzole, memantine, minocycline) may be effective.^{5, 6} Second, riluzole and memantine have shown promise for OCD in case reports or open trials, ⁷⁻ ⁹ but neither is FDA-approved for use in children; riluzole also has significant liabilities in terms of adverse events and cost. ¹⁰ In contrast, ketamine is FDA-approved for anesthesia and chronic pain in children, adolescents and adults, and is routinely used at higher doses than proposed in this study. ¹¹ It is also used as adjunctive pain management for children and adolescents suffering from end stage medical illness.¹²⁻¹³ Third, we found in a small randomized controlled trial that unmedicated OCD adults had a near cessation of obsessional thoughts during an intravenous ketamine infusion; these effects were maintained in half of the patients for up to one week.¹⁴ These exciting findings lead to two questions: 1) is this type of study acceptable and feasible in youth; 2) are ketamine's effects similar in adolescents and young adults? This proof-of-concept study has the potential to pave the way to rapid-acting treatment strategies for adolescents and young adults with OCD.

Our decision to allow participants to remain on their prescribed SRI medications during the study is based on a review of the literature. There are no known interactions between these medications. Additionally, three published psychiatric studies have allowed patients to concurrently take antidepressant medications and ketamine.¹⁵⁻¹⁷ These studies have a combined sample size of 92 participants, and there were no related adverse events. Refer to the uploaded chart titled "SRI - Ketamine Literature Summary" for more information.

Specific Aims and Hypotheses

Specific Aims and Hypotheses

Specific Aims:

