The goal of this proof-of-concept study is to investigate the effect of ketamine on the symptoms of OCD in adolescents and young adults ages 14-22. The symptoms of OCD are evaluated using a number of validated scales designed to measure their clinical status. The specific aims of the study are as follows:

Aim 1. To assess the acceptability, feasibility and tolerability of a single ketamine infusion in adolescents and young adults with OCD.

Aim 2. To assess the effects of ketamine on OCD severity.

Primary Hypothesis:

Adolescent and young adult OCD patients will have a reduction in OCD symptoms immediately following the ketamine infusion.

Description of Subject Population

Sample #1

Specify subject population Individuals with obsessive-compulsive disorder Number of completers required to accomplish study aims 10 Projected number of subjects who will be enrolled to obtain required number of completers 20

Age range of subject population 14-22 inclusive

Gender, Racial and Ethnic Breakdown

Based on our experience and the demographics of the catchment area served by our institution, we expect the subject racial distribution to be approximately 73% White, 18% Black, 9% Asian, and for the ethnic distribution to be approximately 22% Hispanic. We expect the sample to be 50% female. Description of subject population

We will recruit 10 adolescents and young adults (post-pubertal, ages 14-22) with OCD using similar criteria as in the prior study in adults ¹⁴ with the modification that participants have had at least one adequate trial of an SRI medication and a course of CBT for OCD. They will be free of medication or on a stable dose of an SRI medication, score \geq 16 on the Children's Yale-Brown Obsessive Compulsive Scale (CYBOCS) prior to entering the study and report at least moderate severity of obsessions and/or compulsions.

Recruitment Procedures

Describe settings where recruitment will occur The study will recruit participants from the Anxiety Disorders Clinic (ADC), directed by [name], as

well as the CAPES Evaluation Service and the Children's Day Unit (CDU), which are directed by [name]. The ADC screens over 200 adults (\geq 18) with OCD a year. The CAPES/CDU provides free expert consultation, evaluation, and treatment referrals for children and adolescents suffering from mood and anxiety disorders. OCD self-help organizations such as the International OCD Foundation will be contacted to further publicize the existence of this study.

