5 ANALYSIS SET

This pilot study is a non-controlled clinical trial consisting of one group of participants. Participants will be adolescents and young adults with OCD who have failed at least one trial of standard treatment. All participants will receive an intravenous ketamine infusion.

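### The revised SAP keeps an outdated size and population (5, ages 14-20, unmedicated) and analyses neither of the protocol's two response outcomes

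*SAP*

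**What the plan says.** The SAP file holds an initial and a revised version. Section 8.2 of the revised version says the plan was changed after the study was complete and the data had been considered.

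**Size and population.** Section 3 of the revised SAP opens with "We will recruit 5 adolescents and young adults (post-pubertal, ages 14-20) with OCD using similar criteria as in our prior ketamine study". It continues: "They will be free of medication and have at least moderate OCD severity". On entry rules it says that "participants have attempted at least one trial of a standard treatment (i.e., SRI and/or CBT", and it asks for a CY-BOCS rating "of at least 16) and near constant obsessions".

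The protocol, under Description of Subject Population, states: "Number of completers required to accomplish study aims 10 Projected number of subjects who will be enrolled to obtain required number of completers 20". It gives the age range as 14-22 and says of medication: "They will be free of medication or on a stable dose of an SRI medication". Background & Rationale explains "Our decision to allow participants to remain on their prescribed SRI medications during the study" by a review of the literature.

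**Response outcomes.** In the CYBOCS entry of Assessment Instruments, the protocol names two secondary outcomes: response, a decrease of at least 30%, and excellent response, a score of 10 or less. Section 6 of the revised SAP lists only changes in CY-BOCS, CGI-S, OCD-VAS and Y-BOCCS from baseline to day 14. Section 8.1 describes every primary and secondary outcome as continuous.

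**The concern.** The revised SAP governs the final analysis, so its account of the planned sample should match the protocol. As it stands, the two documents give different sizes and entry rules for the same participants. SRI status and age determine whom any observed change describes. The first aim concerns feasibility, so whether the required 10 completers were reached is itself a result, and the revised SAP does not say.

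The second part matters more. An analyst who follows the revised SAP exactly will never compute two outcomes that the protocol names. The revision was made with the data in view and explains only the change of test, so a reader of the results could not tell that response proportions had once been planned and then left out.

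**Working it through.** **1. Population text side by side.**

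| Item | Revised SAP, section 3 | Protocol |
|---|---|---|
| Size | 5 to be recruited | 10 completers (Description of Subject Population) |
| Age | 14-20 | 14-22 (same section; inclusion criterion 1) |
| Medication | None, no exception | None, or a stable SRI (same section); SRIs exempt from washout (criterion 7) |
| Prior treatment | SRI, CBT, or both | An SRI trial and a CBT course, with an exception for CBT (criterion 6) |
| Severity | CY-BOCS 16 or more, with obsessions almost continuous | CYBOCS 16 or more, with obsessions, compulsions or both of moderate severity or worse (criterion 5) |

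**2. Where the SAP text comes from.** Section 3 of the initial SAP has the same size, age, medication, prior-treatment and severity wording. The assessment sentences that follow do differ: the revised version adds the Y-BOCCS, CGI-S and 3-month ratings and drops the depression scale. The section was therefore edited while its population sentences were carried over.

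**3. Response outcomes traced.**

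| | Protocol | Initial SAP | Revised SAP |
|---|---|---|---|
| Percentage fall | 30% or more | 35% or more (8.2 methods text only) | None |
| Low final score | 10 or less | 12 or less (8.2 methods text only) | None |

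The initial SAP's own outcome list (6.1, 6.2) did not include these proportions. Section 8.2 of the revised SAP mentions the replaced mixed model but not the dropped proportions.

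**4. Background: could the initial SAP's cut-offs stand in for the protocol's?** Take whole-number baselines b from the entry minimum of 16 up to an assumed maximum of 40. Points of decrease needed = 0.30b or 0.35b, rounded up.

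| b | 30% rule | 35% rule |
|---|---|---|
| 16 | 4.8, so 5 | 5.6, so 6 |
| 17 | 5.1, so 6 | 5.95, so 6 |
| 26 | 7.8, so 8 | 9.1, so 10 |
| 40 | 12 | 14 |

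The rules agree only at b = 17; at the other 24 of 25 values the 35% rule needs 1 or 2 more points. The assumed maximum does not drive this: from b = 20 upward the gap 0.05b is at least 1, so the rounded values always differ. Example: 26 falling to 18 is (26 - 18)/26 = 30.8%, a response under the protocol but not at 35%. Final scores of 11 and 12 met the initial SAP's remission rule but are not excellent response under the protocol.

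**5. Precision of the missing table.** The exact (Clopper-Pearson) 95% limits are the 2.5% point of Beta(x, n-x+1) and the 97.5% point of Beta(x+1, n-x). For 2/5 this gives 5.3% to 85.3%; for 5/10, 18.7% to 81.3%. These counts are illustrative.

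**The case against.** The best defence is that little of this changes a result. Neither document has a sample-size calculation, no analysis uses the 5, and the revised plan runs paired t-tests on whatever pairs exist. That stands: the size and population mismatch is one of consistency, with no numerical effect on the tests. It is also true that the 35% and 12 cut-offs belong to superseded text, so nobody is reclassified under the plan in force. That arithmetic only shows why the initial SAP never covered the protocol's outcomes.

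Several stronger readings are tempting, and the documents do not support them:

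- A reader might infer that the 5 is the number finally reached, because the protocol's progress report shows 5 enrolled. The initial SAP already gave 5 as its recruitment target, so the figure is inherited.
- A reader might see the SAP contradicting itself, since its Analysis Set section says "Participants will be adolescents and young adults with OCD who have failed at least one trial of standard treatment" while section 3 speaks of an attempted trial. A failed trial was also attempted, and the protocol varies its own wording in the same way.
- A reader might set the approved size of 10 against the 20 projected to enrol. The protocol explains the 20 as the enrolment needed for 10 completers, and the approved 10 may be counted on another basis.
- A reader might say that listed SAP outcomes vanished. The proportions were only ever in the initial SAP's methods text. The fair statement is that their removal is not named.

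None of this answers the remaining point: the protocol itself calls the two response measures secondary outcomes, and no version of the SAP analyses them as defined there.

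**Conclusion.** The point holds in two parts. First, the revised SAP describes a sample that differs from the protocol's in size (5 against 10), age (14-20 against 14-22), medication status, prior treatment and severity. This is a documentation fault. Second, two of two protocol-named response outcomes have no analysis in the revised SAP, and the initial SAP's nearest equivalents used other cut-offs and were dropped without mention in a revision made with the data in view. This is the more serious part and should be put right before results are reported.

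The timing rests on section 8.2 of the revised SAP together with the differences between the two versions of section 3; no separate date is given for that section's edit. The cut-off comparison assumes whole-number CYBOCS totals.

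**What to change.** - **SAP section 3 and Analysis Set section:** reconcile size, age range, medication status, prior treatment and severity with the protocol. Which clinical rule applies is for the sponsor to settle. State whether the 10 required completers were reached, and give the actual number analysed at day 14.
- **SAP sections 6.2 and 8.2:** add response and excellent response as the protocol defines them, as x/n with an exact 95% interval at day 14, the revised plan's analysis day. Day 7 is optional, since the protocol names no analysis day for these outcomes. Label both as added to the SAP after study completion.
- **SAP section 8.2:** declare that the initial SAP's responder and remitter proportions were dropped after study completion.

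The cost is some wording and one small descriptive table from CYBOCS visits already scheduled, with no extra participants or visits. The intervals will be wide, so the table should be read as description only.

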5 ANALYSIS SET

This pilot study is a non-controlled clinical trial consisting of one group of participants. Participants will be adolescents and young adults with OCD who have failed at least one trial of standard treatment. All participants will receive an intravenous ketamine infusion.

6 OUTCOMES

6.1. Primary Outcomes

Primary outcomes will be the changes in the CY-BOCS total score and CGI-S rating from baseline to 14 days post infusion.

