At the conclusion of each test day (after the 2-hour observation period), the study MD will evaluate the patient to determine if the effects of the study drug infusion have resolved to the point that subjects are safe to return home. These evaluation criteria will consist of absence of significant deviations from baseline in vital signs, gait, mental status exam, and assessments listed in the study flowchart including BPRS and CADSS scales. In the case of an adverse psychiatric event, patients will be admitted either to the Pediatric Emergency Department at New York Presbyterian Hospital or directly to the fourth floor inpatient unit (4 Center) at the New York State Psychiatric Institute, if clinically appropriate. The PALS-certified pediatrician will be available for the duration of the post-infusion 2-hour observation period. Once patients have been cleared by the MD to go home, adolescents will be required to leave the Irving Center with a parent or guardian and young adults will be required to leave the Irving Center with a parent or guardian or support person identified by the young adult.

Day 2 – 14: Post-Infusion Monitoring & Assessments

After the ketamine infusion, participants will be monitored closely for a 2-week period. The primary measure of change in OCD symptoms will be the Children's Yale-Brown Obsessive Compulsive Scale (CYBOCS). This, along with additional measures will be administered during this 2-week period as follows:

• *Days 2-6 post-infusion:* OCD-VAS and YBOCCS are administered during optional daily phone calls (except when they have an in-person visit on day 3 or 4, during which these will be administered in person).

The in-person visit between day 2-6 post infusion is not a required study visit and will be offered on a caseby-case basis. During this period, if the study MD determines that an in-person visit is needed or if the participant requests an in-person appointment, they will be asked to come to the clinic and will complete the following assessments. Otherwise these assessments will be completed over the phone.

- Day 3 or 4: Participants come to the CDU to complete the following assessments:
 - MD ratings: Columbia-Suicide Severity Rating Scale (C-SSRS), Young Mania Rating Scale (YMRS), Clinician Administered Dissociative States Scale (CADSS), Brief Psychiatric Rating Scale (BPRS), Clinical Global Impressions Scale (CGI).

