Yale-Brown Obsessive Compulsive Scale, Child version (CYBOCS): The CYBOCS is a semi-structured measure of OCD severity with excellent inter-rater reliability, internal consistency, and test-retest reliability. It is validated in those starting at age 7 and used in studies up to age 20. The CYBOCS differs from the adult YBOCS only in its use of simpler language. The CYBOCS will be administered by IE at screening and 120 minutes post-infusion to determine OCD severity. The CYBOCS will also be administered by IE at baseline, day 7, and day 14 and will be the primary outcome measure. As secondary outcomes, response will be defined as a CYBOCS decrease of \geq 30% and excellent response as a CYBOCS of \leq 10 following the Pediatric OCD Treatment Study (2004). The CYBOCS checklist will be used to determine symptom dimensions.

Children's Depression Rating Scale-Revised (CDRS-R): The CDRS-R is a 17-item clinician-administered semi-structured interview with good inter-rater reliability and validity that assesses 17 symptom areas related to depression, including those that serve as criteria in the DSM-IV. It provides an overall index of severity of depression. This assessment will be administered by IE at screening and 120 minutes post-infusion and by IE at baseline, day 7 and day 14.

Clinical Global Impressions Scale (CGI): This is a clinician rated instrument providing a single score for severity and improvement (from a 7-point scale) comparing the patient's condition during each visit on treatment to the condition at baseline (before treatment). The CGI will be administered by both IE and the study MD as per the study flow chart.

Columbia-Suicide Severity Rating Scale (C-SSRS): This is a semi-structured clinician rating of suicidal behavior, suicide attempts, and presence and intensity of suicidal ideation. The assessment will be administered by study MDs at screening, baseline, day 3 or 4, day 7, and day 14.

Young Mania Rating Scale (YMRS): YMRS is an 11- item clinician administered scale for rating manic symptoms. It will be administered by the study MD at baseline, 120 minutes post-infusion, day 3 or 4, day 7, and day 14.

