8.1. Descriptive Statistics

All primary and secondary outcomes are continuous variables and descriptive statistics will be reported by mean and standard deviation.

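### The revised SAP makes CGI-S change a second primary outcome beside the protocol's CY-BOCS, with no either/both rule, no adjustment and no named CGI-S rater

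*SAP*

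**What the plan says.** **Protocol.** The section on Days 2-14 states "The primary measure of change in OCD symptoms will be the" CYBOCS. Assessment Instruments repeats it: "The CYBOCS will also be administered by IE at baseline, day 7, and day 14 and will be the primary outcome measure". The CGI is nowhere called primary. On who rates it, Assessment Instruments says "The CGI will be administered by both IE and the study MD", and the day 7 and day 14 visit lists show it under both raters. The Baseline Evaluation list includes the CGI without naming a rater.

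**Initial SAP (Outcomes, 6.1 and 6.2).** The primary outcomes are the numbers screened and completing. CY-BOCS and the depression scale are secondary. CGI-S is not listed.

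**Revised SAP.** Section 6.1 names as primary the "changes in the CY-BOCS total score and CGI-S rating from baseline to 14 days post infusion". Sections 7 and 8.2 give each outcome a paired t-test with its own confidence interval and p-value. Section 8.2 says the move from a mixed model to t-tests was made after the study ended and the collected data had been considered. Section 8.1 says "All primary and secondary outcomes are continuous variables". The revised SAP states no significance level, hierarchy, adjustment or rule for combining the two primary results, and names no CGI-S rater.

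**The concern.** The three documents give three different sets of primary outcomes, and the last was set down when the data were already known. With two primary tests and no rule, a positive result on either can be reported as a positive primary result. The CGI-S outcome also has two candidate values at day 14, one per rater, and a change score could take its baseline from one rater and its day 14 value from the other.

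This matters even in a small pilot. Both the protocol and the SAP say that promising data will support a grant application for a full-scale randomised trial, so a reader needs to know which outcome and which rater define the primary result.

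**Working it through.** The documents give no alpha, power or familywise error figure, so there is nothing to reproduce. The inputs are:

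- Two primary tests, both paired t-tests (revised SAP 6.1, 8.2).
- n = 5 (revised SAP, Procedures). The protocol's continuing-review page reports 4 completers, and its target is 10.
- **Assumed:** two-sided 5% per test, in line with the 95% confidence intervals.
- **Assumed:** either test may carry the claim.
- **Assumed:** correlation between the two changes of 0.5 to 0.9. No value is given, but both scales rate severity in the same patients at the same visits.

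**1. Limits for two tests.**
- Independent tests: 1 - 0.95² = 0.0975.
- Upper bound for any correlation, if each test holds 5%: 0.05 + 0.05 = 0.10.
- If both tests must be significant: at most 0.05, so no inflation.

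**2. Correlated tests.** Pairs of t-tests on bivariate normal changes with no true effect, 400,000 simulated trials per case, chance that at least one is significant:

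| Correlation | n = 4 | n = 5 | n = 10 |
|---|---|---|---|
| 0.5 | 9.4% | 9.3% | 9.1% |
| 0.7 | 9.0% | 8.9% | 8.6% |
| 0.8 | 8.6% | 8.3% | 8.0% |
| 0.9 | 7.9% | 7.6% | 7.3% |

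At n = 5 this is about 7.5-9.5%, or roughly 1.5 to 1.9 times the nominal 5%.

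**3. Allowing for integer CGI-S changes.** Suppose that, with no true effect, changes are -1, 0 or +1 with probabilities 0.2, 0.6, 0.2 (assumed).
- At n = 5 the critical t is 2.776. Four changes of +1 and one of 0 give mean 0.8, SD 0.447, t = 0.8/(0.447/√5) = 4.0, which is significant. Three of +1 and two of 0 give t = 2.45, which is not. Only the four-and-one pattern, in either direction, reaches significance: 2 × 5 × 0.2⁴ × 0.6 = 0.0096, about 1.0%.
- With 0.25, 0.5, 0.25: 2 × 5 × 0.25⁴ × 0.5 = 0.0195, about 2.0%.
- At n = 4 the critical t is 3.182. The most extreme defined pattern (three of +1, one of 0) gives t = 0.75/0.25 = 3.0, so the error is 0%.
- Adding the CY-BOCS test at 5%, the total at n = 5 is at most 5% + 1.0% = 6.0% or 5% + 2.0% = 7.0%, and at n = 4 at most 5%.
- A wide spread works the other way. Changes uniform on -2 to +2 give 7.0% for the CGI-S test alone at n = 5, so that test no longer holds its nominal level and the 10% bound in step 1 does not apply.

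**4. When the t-test cannot be computed.** If all changes are equal, t is undefined. For changes 0, -1, -2 with assumed probabilities 0.2, 0.6, 0.2, this happens with probability 0.6⁵ + 2 × 0.2⁵ = 7.8% at n = 5 and 0.6⁴ + 2 × 0.2⁴ = 13.3% at n = 4. With 0.3, 0.5, 0.2 it is 3.4% and 7.2%. These are illustrations only, since the documents give no distribution of changes.

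**5. Rater.** This is not part of step 2. If both raters' CGI-S changes could also be tested separately, there would be three tests: 14.3% if independent, and 13.3% to 9.4% at n = 5 for equal correlations of 0.5 to 0.9. The SAP does not provide for three tests; this shows only what an unnamed rater leaves open.

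**The case against.** The revised SAP states no alpha or success criterion, and section 7 presents the tests as a way to describe changes. The trial is an uncontrolled pilot, so even perfect error control would not turn a pre-post change into evidence of a drug effect. If both outcomes had to succeed, there would be no inflation. All of this stands. It limits how much weight the percentages can bear, but it does not supply the missing rule or the missing rater.

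Three stronger readings are tempting and are not supported:

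- **That the false positive rate about doubles.** That needs near-independence (9.75%), the least plausible case for two severity ratings of the same patients at the same visit. It also treats integer CGI-S changes as continuous.
- **That having two raters is part of the two-test inflation.** The CY-BOCS outcome measure is rated by the IE alone. The rater question concerns which CGI-S value is used and is a separate defect.
- **That CGI-S was made primary because its result was favourable.** The revised SAP says only that the test was changed after the data were considered. It gives no reason for the change of outcomes. Nor was CGI-S alone promoted: CY-BOCS also moved up from secondary in the initial SAP, in line with the protocol.

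The study flowchart, which the protocol cites for CGI ratings, is not among the documents, so it may settle who rated the CGI at baseline. It cannot tell the reader which rating the SAP means to analyse.

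**Conclusion.** The point holds in moderate form. The revised SAP departs from the protocol's single primary outcome measure and leaves open which outcome, and which rater, can carry the primary claim.

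Under a two-sided 5% level and an either-outcome rule, both assumed, the chance of a false positive at n = 5 is roughly 7.5-9.5% instead of 5% for correlations of 0.5 to 0.9. It is lower if CGI-S changes span only a few integer values. The larger problem cannot be quantified from the documents: these rates are for tests fixed in advance, whereas this plan was revised with the data in hand. The unnamed rater and the description of a 7-point rating as continuous are defects whatever view is taken of multiplicity. Calling CGI-S continuous is the least important of these.

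**What to change.** In the revised SAP:

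1. Make CY-BOCS change the single primary efficacy outcome, as in the protocol. State openly that the initial SAP had feasibility counts as primary and CY-BOCS as secondary, and report those counts.
2. Make CGI-S change secondary. Use the same rater at baseline and day 14: the IE if an IE baseline rating exists, otherwise another stated rater who has both. Give the other rater's result as a sensitivity analysis.
3. Report CGI-S as a shift table or a median change, and correct the sentence in 8.1 that calls every outcome continuous.
4. Label the p-values post hoc and descriptive.

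If the sponsor prefers to keep both outcomes primary, the SAP should state the either/both rule. For an either rule it should add an adjustment such as Holm or Bonferroni; 2.5% each gives 1 - 0.975² = 4.9% if independent and at most 5% otherwise, provided each test holds its level.

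The cost is SAP wording only, with no new data collection. CGI-S loses primary status. None of this undoes the fact that the analysis was chosen after the data were seen, which is why the labelling in item 4 is needed.
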